The Investigator and study staff will also use the Harbor-UCLA Medical Center's Electronic Medical Records to screen for potential subjects. Additionally, the Investigator and study staff will review clinical cultures from the Harbor-UCLA Microbiological Laboratory to identify wound cultures growing *gram positive organism* and review the Electronic Medical Record to identify those cultures that were taken from bone and joint infections.

After identifying a potential patient, the Investigator or study staff will approach the subject's primary treatment team and ask for their permission to introduce the study and the study staff to the patient. Study staff will then present information about the study (See Recruitment Script V1.0) to see if they are interested. Permission will be sought from the subject by their primary treatment team before anyone outside the patient's primary treating team approaches them about the study.

Describe the source of subjects.

Subjects presenting to the Emergency Department, inpatient Units ,Outpatient Clinics or referred by a community physician with bone and joint infection will be recruited.

Describe the methods that will be used to identify potential subjects.

PROTOCOL TITLE: *Tolerability, Safety, and Efficacy of Tedizolid as Oral Treatment for Bone and Joint Infection*

Revised: 8/10/18 Version 1.6

Either the Investigator, [name], who is an attending physician of Internal Medicine and Infectious Diseases, or other study staff or staff members of Harbor-UCLA Medical Center will identify potential subjects based on a clinical culture, chart review or diagnosis of bone and joint infection. The providers will first ask the subject for permission before any non-treatment team members of the study staff can approach the subject.

Describe materials that will be used to recruit subjects. Include copies of these documents with the application. For advertisements, submit the final copy of printed advertisements. When advertisements are taped for broadcast, provide the final audio/video tape. You may submit the wording of the advertisement prior to taping to preclude re-taping because of inappropriate wording, provided the HSC reviews the final audio/video tape.

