The secondary study endpoint is the safety of prolonged (≥ 4 weeks) courses of tedizolid antibiotic therapy for patients with bone and joint infection. CBC and a CMP (comprehensive chemistry panel including liver function tests) will be performed at the following intervals after initiation of tedizolid. We will administer standardized surveys about drug side effects at all follow visits (weeks 1, 2, 3, 4, 5, 6 (optional), 7 (optional), 8 (optional), 9 (optional), 10 (optional), 11 (optional), 12). Adverse events will be measured using the Medical Dictionary for Regulatory Activities Terminology (MedDRA) version 18.1 (or the most current version).

The tertiary study endpoint is efficacy, which will be defined using criteria as determined by the subject's primary provider. Specifically, cure will be defined as no need for further antibiotics beyond the originally planned duration (i.e., 6 weeks for non-device associated bone and joint infection or until hardware removal for subjects with implants). Unplanned surgical procedures prompted by inadequate infection control will be categorized as treatment failure. We will also measure long-term efficacy by performing a phone survey 3 months after completion of antibiotics. Recurrence of signs or symptoms of bone and joint infection will be considered a long-term treatment failure. Confirmation of subjects self-report with medical record review will be performed on an as needed basis when categorization of self-reported outcomes is not clear.

g) Procedures Involved in the Human Research*

Describe and explain the study design.

The design of this study is a prospective, open-label, non-comparative clinical trial of tedizolid for the treatment of bone and joint infection. We will follow patients for between 16 and 24 weeks, depending on the length of their antibiotic treatment, for the purpose of determining tolerability, safety, and efficacy of prolonged use (≥ 4 weeks) of tedizolid in the treatment of bone and joint infection. Participants will be enrolled regardless of race, ethnicity, or gender (as long as they are within 18-85 years of age).

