Once informed consent is obtained, we will collect data on all subjects' demographics, co-morbidities, surgical history, pertinent microbiology results, and all concomitant medications using standardized forms. For exclusion criteria e) and f) regarding cytopenias and liver function, CBC/CMPs from the past 14 days will be evaluated through a medical chart review. Note that if a CBC has not been performed within the past 14 days, a CBC will be performed on the day of enrollment prior to any study drug being administered to ensure the patient does not meet exclusion criteria (see exclusion criteria e) and f)).

Upon confirmation of eligibility, the study coordinators will call the pharmacy, which will be the LA BioMed Investigational Drug Service (IDS). The research pharmacists at the LABioMed Investigational Drug Service (IDS) will dispense the medication to the subject. Subjects will be given detailed verbal instructions on the use of the medication in either English or Spanish as preferred by the subject. The subject will be given a medication diary and asked to record the time of day when they take each pill as well as any side effects or comments. The subject will be given a small card to keep on their person with information about the study and study staff and emergency contact information. The study staff will answer any questions that the subject has at this time and will encourage the subject to contact the study staff with any future questions.

The subject will present to the Clinical and Translational Research Unit (CTR), the clinical site of the UCLA Clinical and Translational Science Institute (CTSI) on the Harbor-UCLA campus for follow up visits. These follow up visits will occur at week 1, week 2, week 3, week 4, week 5, week 6, week 7, week 8, week 9, week 10, week 11, week 12 and week 13. All subjects will return for follow up visits on weeks 1 – 5 and 12, and subjects still taking the study drug after week 5 will continue to return for weekly follow up visits until they complete the course or until they reach 12 weeks. Once subjects complete the course of the study drug, they will return for one additional weekly follow up visit (e.g. if a patient completes the study drug at 7 weeks, they will return for visits on weeks 1-8 and week 12). If subjects take the study drug for 12 weeks, they will return for a final follow up visit on week 13.

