At each follow up visit, CBC and CMP (comprehensive chemistry panel including liver function tests) will be collected via a blood draw. This blood sample will be sent to Quest Diagnostics by the

PROTOCOL TITLE: *Tolerability, Safety, and Efficacy of Tedizolid as Oral Treatment for Bone and Joint Infection*

Revised: 8/10/18 Version 1.6

CTSI/CTRU, an outside laboratory that is contracted with the CTSI/CTRU to process blood samples. Additionally, standardized surveys (See Data Collection Fields V 1.0, Neuropathy Scale V 1.0, attached) will be administered about drug side effects and tolerability, and adverse events will be measured using the Medical Dictionary for Regulatory Activities Terminology (MedDRA) version 18.1 (or the most current version). At these follow up visits, we will also record data points relevant to defining the efficacy of the treatment, such as the duration of the antibiotic treatment, any unplanned surgical procedures prompted by inadequate infection control, recurrence of signs or symptoms of bone and joint infection, and any other relevant comments or observations from the subject. The subject will also be asked to bring their study drug medication bottle and medication diary in order to assess compliance. If a subject suspects pregnancy during a follow up visit, they will be given a pregnancy test and the study team will track their reported menstrual cycle. If the subject does become pregnant, they will be discontinued from the study drug. Study staff will follow and collect data on the course of the pregnancy and the health of the child for at least 6-8 weeks after delivery.

Patients with evidence of myelosuppression will continue to have weekly CBCs performed until resolution of the myelosuppression.

Subjects who are concurrently taking serotonergic agents while receiving the study drug will be monitored for signs and symptoms of serotonin syndrome at each scheduled follow-up visit. Symptoms of serotonin syndrome include agitation or restlessness, confusion, rapid heartbeat and high blood pressure, dilated (big) pupils, loss of muscle coordination or twitching muscles, muscle rigidity (stiffness), heavy sweating, diarrhea, headache, shivering and goose bumps.

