The subjects will be paid in cash for their follow up visits. They will be paid \$30 for the visit on week 1, \$35 for the visit on week 2, \$40 for the visit on week 3, \$40 for the visit on week 4, \$45 for the visit on week 5, \$45 for the visit on week 6, and \$50 each visit for visits on weeks 7, 8, 9, 10, 11, 12 and 13.

The total amount of compensation will range between \$240 and \$585 based on the number of follow up visits the subject completes. All subjects will complete visits on Weeks 1,2,3,4,5, and 12. Subjects still taking the study drug at week 6 will be required to return for a Week 6 follow up visit. Subjects still taking the study drug at week 7 will be required to return for a week 7 follow up visit, and so on- while patients are receiving the study drug they will return for weekly follow up visits until they have completed the course, or until they have reached 12 weeks. Once subjects complete the course of the study drug, they will return for one additional weekly follow up visit (e.g. if a patient completes the study drug at 7 weeks, they will return for visits on weeks 1-8 and week 12). If subjects take the study drug for 12 weeks, they will return for a final follow up visit on week 13.

A phone survey 3 months after the subject's completion of antibiotics will be performed. They will be asked about their overall well-being, recurrence of signs or symptoms of bone and joint infection and any self-reported medical conditions or adverse events (medical record review will be performed on an as needed basis when categorization of self-reported outcomes is not clear).

Provide a description of all procedures being performed and when they are performed, including procedures being performed to monitor subjects for safety or minimize risks. Include procedures

PROTOCOL TITLE: *Tolerability, Safety, and Efficacy of Tedizolid as Oral Treatment for Bone and Joint Infection*

Revised: 8/10/18 Version 1.6

being performed already for diagnostic or treatment purposes and differentiate between these and the procedures performed solely for the research.

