The study is descriptive and thus no formal statistical analysis plan has been performed. The number of subjects chosen (n=50) is based on a sample size believed to have sufficient power to reassure clinicians that tedizolid is safe, tolerable, and efficacious for the treatment of native bone and hardware-associated bone and joint infection.

Of note, confidence intervals for safety and efficacy will be calculated. Confidence intervals for outcomes of low incidence (e.g., thrombocytopenia) will be approximately +/-3 - 7%. E.g., assuming n=50 subjects, a low incidence outcome with a probability of 2.5% will have 95% confidence intervals of <0.1%-6.8%. Outcomes with probabilities farther from 0% or 100% will have wider confidence intervals. For example, we anticipate cure rate will be 80%, in which assuming n=50, 95% confidence intervals will be 69%-91%.

Provide a power analysis.

Confidence intervals for safety and efficacy will be calculated. Confidence intervals for outcomes of low incidence (e.g., thrombocytopenia) will be approximately +/-3 - 7%. E.g., assuming n=50 subjects, a low incidence outcome with a probability of 2.5% will have 95% confidence intervals of <0.1%-6.8%. Outcomes with probabilities farther from 0% or 100% will have wider confidence intervals. For example, we anticipate cure rate will be 80%, in which assuming n=50, 95% confidence intervals will be 69%-91%.

Describe the steps that will be taken to secure the data (e.g., training, authorization of access, password protection, encryption, physical controls, certificates of confidentiality, and separation of identifiers and data) during storage, use, and transmission.

All source documents and specimens will be coded meaning these items will be labeled the subjects Study ID number and will include dates (case report forms) rather than his/her name and/or date of birth. We will maintain a separate password-protected key list/log (electronic file) linking each subject to their Study ID and a hardcopy will be maintained separate from individual subject files in a separate locked filing cabinet. Access to study computers and files will be limited to study personnel. Human research records including Informed Consent Forms

PROTOCOL TITLE: *Tolerability, Safety, and Efficacy of Tedizolid as Oral Treatment for Bone and Joint Infection*

Revised: 8/10/18 Version 1.6

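### Three-month recurrence rests on a phone self-report that is checked against records only when unclear, which leaves the long-term success rate open to misclassification and missing-outcome bias, possibly but not certainly upward

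*Combined protocol and SAP*

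**What the plan says.** Section 9(f), Study Endpoints, makes efficacy the tertiary endpoint. Its long-term part is described as follows: "We will also measure long-term efficacy by performing a phone survey 3 months after completion of antibiotics". The failure criterion is broad: "Recurrence of signs or symptoms of bone and joint infection will be considered a long-term treatment failure". Verification is conditional: "Confirmation of subjects self-report with medical record review will be performed on an as needed basis when categorization of self-reported outcomes is not clear". Section 9(g), Procedures, describes the call as covering general well-being, recurrence, and self-reported conditions or adverse events, and repeats the rule: "medical record review will be performed on an as needed basis when categorization of self-reported outcomes is not clear".

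Recurrence is also asked about in person. Section 9(g) lists, among the data recorded at follow-up visits, "recurrence of signs or symptoms of bone and joint infection, and any other relevant comments or observations from the subject". All subjects attend at week 12, and "If subjects take the study drug for 12 weeks, they will return for a final follow up visit on week 13".

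Section 9(c) continues enrolment until 50 evaluable subjects have finished follow-up to week 12. The three-month call is not part of that definition. Section 9(i), Data Management, states that the study is descriptive and has no formal statistical analysis plan. It gives one efficacy figure: "we anticipate cure rate will be 80%, in which assuming n=50, 95% confidence intervals will be 69%-91" per cent. The protocol text does not say how many call attempts are made, whether records are searched for subjects who are not reached, or how such subjects are counted.

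**The concern.** Whether an outcome is verified depends on how the answer sounds, not on a rule applied to everyone. Three kinds of error can pass through:

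- **Missed recurrence.** The call as described does not name new antibiotics or surgery. A subject who was retreated elsewhere and is now well could answer no, and would count as a success.
- **False recurrence.** The criterion is any return of signs or symptoms. A subject with pain from another cause could answer yes, and would count as a failure.
- **No answer.** An unreached subject supplies nothing to be unclear about, so no review is triggered and no rule says how to count the outcome.

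There is one open-label arm, so no comparator exists in which similar errors might cancel. Efficacy is in the title and is the third hypothesis in section 4. Section 9(i) also says the sample size was chosen partly to reassure clinicians that the drug works. With 50 subjects, each wrongly classified outcome moves the rate by 1/50 = 2 percentage points, and the planned confidence interval reflects sampling error only.

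**Working it through.** **1. The plan's own figure.** Inputs from section 9(i): p = 0.80, n = 50. The Wald interval is p ± 1.96 × √(p(1−p)/n) = 0.80 ± 1.96 × √(0.16/50) = 0.80 ± 0.111, or 68.9% to 91.1%. This reproduces the stated 69% to 91%. The figure is for cure in general, which section 9(f) defines by need for further antibiotics and unplanned surgery. The protocol gives no rate for three-month recurrence, so 80% is only a convenient baseline below.

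**2. How much of the window the visits cover.** Courses last 4 to 12 weeks.

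- 4-week course: last visit at week 12, which is 12 − 4 = 8 weeks after the last dose.
- 11-week course: last visit at week 12, which is 1 week after.
- 12-week course: last visit at week 13, which is 1 week after.

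Taking three months as about 13 weeks, the stretch covered by the call alone runs from 13 − 8 = 5 weeks to 13 − 1 = 12 weeks. It is longest after the longest courses.

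**3. Misclassification.** Let Se be the share of true recurrences reported and Sp the share of true successes reported as free of recurrence. Both are assumptions; the protocol gives neither.

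Apparent success = p × Sp + (1 − p) × (1 − Se), with p = 0.80.

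| Se | Sp | Calculation | Apparent success | Shift (points) |
|---|---|---|---|---|
| 0.9 | 1.00 | 0.80 + 0.20 × 0.1 | 82% | +2 |
| 0.8 | 1.00 | 0.80 + 0.20 × 0.2 | 84% | +4 |
| 0.7 | 1.00 | 0.80 + 0.20 × 0.3 | 86% | +6 |
| 0.8 | 0.95 | 0.76 + 0.04 | 80% | 0 |
| 0.8 | 0.90 | 0.72 + 0.04 | 76% | −4 |

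The net shift is upward only if 0.80 × (1 − Sp) < 0.20 × (1 − Se), that is, if 1 − Sp < 0.25 × (1 − Se). At Se = 0.8 the break-even is 5% false reports among true successes.

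The first three rows treat every recurrence as detectable only by phone. If half had already been recorded at visits (an assumption), the upward shift would halve: 0.20 × 0.5 × 0.1 to 0.20 × 0.5 × 0.3, or 1 to 3 points.

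**4. Unreached subjects.** Suppose 5 of 50 are unreached (an assumption). If 36 of the 45 reached are successes, the observed rate is 36/45 = 80%. Counting all five as failures gives 36/50 = 72%; counting all as successes gives 41/50 = 82%. With 10 unreached and 32/40 = 80% observed, the bounds are 32/50 = 64% and 42/50 = 84%.

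If the true rate is 40/50 and five unreached subjects with recurrence rate f are left out, the reported rate is (40 − 5(1 − f))/45:

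- f = 10%: 35.5/45 = 78.9%
- f = 20%: 36/45 = 80.0%
- f = 40%: 37/45 = 82.2%
- f = 60%: 38/45 = 84.4%

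Omission inflates the rate only when unreached subjects do worse than average.

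**The case against.** The strongest objection is that no direction of bias has been shown. A reader might infer that the design inflates the long-term success rate. The documents do not support that: the failure criterion is broad, an unverified yes lowers the rate, and a modest false-report rate cancels or reverses the effect of missed recurrences. This stands.

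A reader might also infer that unreached subjects leave the denominator. Replacement of non-completers up to week 12 makes that a natural guess, but no rule says so. Nor can the plan's 10% attrition in section 9(c) serve as a loss rate at the call. It concerns completion through week 12, and enrolling about 55 to obtain 50 already allows for it. Both points stand, so the 5 of 50 above is an assumption and not the plan's figure.

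Visits do capture early recurrence, for more than half of the window after a 4-week course. This narrows the gap without closing it, least of all after long courses. The survey form is an attachment not included in the document, and it may ask more than section 9(g) describes. Even so, the verification rule and the silence on unreached subjects would remain.

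Finally, this is part of a tertiary endpoint in a descriptive pilot with no comparative claim, and a 2 to 6 point shift is smaller than the ±11 point sampling interval. That limits the priority. It does not argue against a cheap remedy, since the interval takes no account of this error.

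**Conclusion.** The point holds as a weakness in outcome ascertainment, not as a demonstrated upward bias. Verification is selective, mistaken answers in either direction go unchecked, and unreached subjects have neither a record check nor a counting rule. Upward bias is realistic: the described call does not name retreatment or surgery, and unreached subjects may do worse than average. It is not certain.

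Under the illustrative assumptions, misclassification moves an 80% rate by anything from −4 to +6 points, and five unreached subjects leave bounds of 72% to 82%. These sizes depend on assumed sensitivity, specificity and loss, and on a baseline borrowed from the general cure figure. The change should be made, but the primary tolerability result does not depend on it.

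**What to change.** In sections 9(f) and 9(g), replace the conditional check with a structured record review for every subject at the three-month point, whatever the self-report:

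- **Content.** Cover new antibiotics, unplanned surgery or readmission for the index site, and documented recurrence. Where care was given outside the site, ask the treating physician.
- **Classification.** Check both yes and no answers against the record under one pre-stated rule. Do not count failure automatically whenever either source suggests it, because that would trade missed recurrences for false ones.
- **Unreached subjects.** Use the record to classify them.
- **Reporting.** State the denominator, and give all-failure and all-success bounds for subjects whose outcome is still unknown.

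The cost is roughly 50 chart reviews plus some physician contacts. Staff already use the hospital's "Electronic Medical Records to screen for potential subjects" (section 9(a)), and also draw on records for eligibility, laboratory and culture data (section 9(g)). Outside care may be missing from that record, which is why the physician contact is needed. The reported rate may turn out slightly less favourable.

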Tedizolid is a FDA approved antibiotic with an indication for skin and soft tissue infection. Its spectrum of activity is nearly all gram positive cocci, i.e., the primary causes of osteomyelitis. Unlike the other commercially available medication in its class, linezolid, tedizolid does not appear to be associated with hematologic and neurologic toxicities in short term and animal studies. However, longer term studies with tedizolid have not been performed.

This study is a pilot study. We realize that efficacy is of primary concern for treatment of bone and joint infection, but the purpose of this study is more exploratory and will focus primary on the tolerability/toxicity issues outlined above.

Additional outcomes will be measured, but these are not primary outcomes. We will measure efficacy of tedizolid, but comparative efficacy (e.g., compared to non-tedizolid based regimens) will not be measured based on small sample size and funding limitations. Of great importance to highlight is that clinical trials, even non-comparative ones, are extremely rare for bone and joint infection. Randomized clinical trials comparing one antibiotic to another for bone and joint infection are almost never performed in the current era.

Hypotheses:

1. Tedizolid is well tolerated for prolonged (≥ 4 weeks) courses of antibiotic therapy for patients with bone and joint infection
2. Tedizolid is safe for prolonged (≥ 4 weeks) courses of antibiotic therapy for patients with bone and joint infection
3. Tedizolid is effective for the treatment of bone and joint infection

5) Background*

Describe the relevant prior experience and gaps in current knowledge.

Describe any relevant preliminary data.

Provide the scientific or scholarly background for, rationale for, and significance of the Human Research based on the existing literature and how will it add to existing knowledge.

PROTOCOL TITLE: *Tolerability, Safety, and Efficacy of Tedizolid as Oral Treatment for Bone and Joint Infection*

Revised: 8/10/18 Version 1.6

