Phase 1 studies conducted in healthy adults exposed to tedizolid (200 mg oral/intravenous once daily) for 21 days showed a possible dose and duration effect on hematologic parameters beyond 6 days of treatment.

Peripheral and optic neuropathy have been described in patients treated with another member of the oxazolidinone class for longer than 28 days. In Phase 3 ABSSI trials, reported adverse reactions for peripheral neuropathy and optic nerve disorders were similar between both treatment arms (peripheral neuropathy 1.2% vs. 0.6% for tedizolid phosphate and linezolid, respectively; optic nerve disorders 3% vs. 0.2%, respectively). No data are available for patients exposed to tedizolid for longer than 6 days.

If applicable, indicate which procedures may have risks to the subjects that are currently unforeseeable.

Use of prolonged tedizolid treatment (4-12 weeks) has not yet been studied or approved by the FDA, which may pose currently unforeseeable risks. However, tedizolid has a favorable adverse event profile and low thrombocytopenia rates compared to linezolid which is approved by the FDA for prolonged antibiotic therapy. Additionally, at FDA-approved doses, tedizolid has

PROTOCOL TITLE: *Tolerability, Safety, and Efficacy of Tedizolid as Oral Treatment for Bone and Joint Infection*

Revised: 8/10/18 Version 1.6

hematologic side effects similar to that of placebo. Additionally, unlike linezolid, interactions with SSRIs appear unlikely. Drug-mitochondrial binding, which is believed to be the mechanism to which mid- and long-term toxicities of linezolid such as neuropathy are acquired, is not seen with tedizolid, suggesting that the side effects associated with long-term therapy of linezolid may not be found with tedizolid. Tedizolid will be used in this research to treat bone and joint infection in patients who need prolonged antibiotic treatment for 4-12 weeks.

Despite these promising initial results, there still may be currently unforeseeable risks. For this reason, Drs. [name] and [name] will closely monitor subject data in monthly reviews, and a Data Safety Monitor ([name]) will review all safety data (including labs, vital signs, results of peripheral neuropathy scales, and all reported adverse events, side effects, complications, or other patient feedback) every three months or after 10 patients have been enrolled, whichever comes first.

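### The sample-size rationale claims sufficient power for 50 subjects, but no criterion or power calculation exists, and the precision offered in its place is too optimistic for rare toxicities

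*Combined protocol and SAP*

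**What the plan says.** Section 9(i), Data Management, opens its analysis plan with "The study is descriptive and thus no formal statistical analysis plan has been performed". It then describes n=50 as a "sample size believed to have sufficient power to reassure clinicians that tedizolid is safe, tolerable, and efficacious", for both native-bone and hardware-associated infection.

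The support given is a paragraph on confidence intervals:

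- about 3 to 7 percentage points either side for low-incidence outcomes, with thrombocytopenia as the example;
- <0.1% to 6.8% for an event with probability 2.5%;
- 69% to 91% for an anticipated cure rate of 80%.

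The form then asks for a power analysis, and the same paragraph is repeated as the answer.

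Section 4, Objectives, says "This study is a pilot study". It calls the purpose exploratory with a focus on tolerability and toxicity, and places efficacy outside the primary outcomes. Section 9(f) ranks efficacy third. The hypotheses in section 4 are nevertheless worded as conclusions, for example "Tedizolid is safe for prolonged (≥ 4 weeks) courses of antibiotic therapy for patients with bone and joint infection".

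Section 10, Risks to Subjects, gives reference rates from 6-day courses. Table 1 there lists low neutrophils at 0.5%, low platelets at 2.3% and low haemoglobin at 3.1%. The text adds "peripheral neuropathy 1.2% vs. 0.6% for tedizolid phosphate and linezolid, respectively". It also reports that 21-day Phase 1 studies "showed a possible dose and duration effect on hematologic parameters beyond 6 days of treatment".

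**The concern.** Power is the probability of meeting a stated criterion when a stated truth holds. The plan gives neither a criterion nor a truth to assume, so the word has nothing behind it. A clinician or ethics committee reading the sentence would take it that 50 subjects had been shown to be enough.

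The toxicities that motivate the trial, hematologic and neurologic, are the ones for which 50 subjects say least if rates are low. Section 5 notes that the neurologic toxicity of linezolid, the other drug in the class, may be irreversible, so the rate that a clean result can exclude matters. The printed interval for a rare event makes that exclusion look tighter than it is.

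**Working it through.** **Inputs.** n = 50, event rate 2.5% and cure rate 80% (section 9(i)). Reference rates of 0.5%, 2.3% and 3.1% (section 10, Table 1) and 1.2% (section 10 text).

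**1. Reproducing the plan's intervals.** The Wald formula is p ± 1.96 × √(p(1−p)/50).

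- p = 0.025: 1.96 × √(0.025 × 0.975/50) = 0.0433, giving −1.8% to 6.8%. The plan prints <0.1% to 6.8%, so the upper limit agrees and the negative lower limit has been cut at zero.
- p = 0.80: 1.96 × √(0.16/50) = 0.111, giving 68.9% to 91.1%. The plan prints 69% to 91%.
- Half-widths run from 2.8 points at 1% to 7.1 points at 7%, which agrees with the stated 3 to 7.

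There is no power figure to reproduce.

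**2. What 50 subjects can exclude.** A rate of 2.5% in 50 is 1.25 expected events, too few for the normal approximation. Exact (Clopper-Pearson) two-sided 95% intervals are:

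| Events in 50 | Exact 95% interval | Wald 95% interval (cut at 0) |
|---|---|---|
| 0 | 0% to 7.1% | 0% to 0% |
| 1 | 0.05% to 10.6% | 0% to 5.9% |
| 2 | 0.5% to 13.7% | 0% to 9.4% |

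For 0/50 the exact upper limit is 1 − 0.025^(1/50) = 7.1%. Since this is the smallest upper limit that 50 subjects can give, no observed count yields an exact two-sided limit as low as the printed 6.8%.

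**3. Chance of seeing no case.** P(0 in 50) = (1 − p)^50.

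| Event (6-day rate) | P(0 in 50) |
|---|---|
| Low neutrophils, 0.5% | 0.995^50 = 78% |
| Peripheral neuropathy, 1.2% | 0.988^50 = 55% |
| Low platelets, 2.3% | 0.977^50 = 31% |
| Low haemoglobin, 3.1% | 0.969^50 = 21% |

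A 95% chance of at least one case needs 1 − (1 − p)^50 ≥ 0.95, so p ≥ 1 − 0.05^(1/50) = 5.8%.

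**4. Power for cure, as an illustration.** No minimum cure rate is stated, so a null value has to be assumed. With a true cure rate of 80%, n = 50 and one-sided alpha of at most 0.025:

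| Assumed null cure rate | Cures needed in 50 | Power |
|---|---|---|
| 60% | 38 | 81% |
| 65% | 40 | 58% |
| 70% | 42 | 31% |
| 75% | 44 | 10% |

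The answer moves from 81% to 10% with a value that the plan does not give. For comparison, 40 cures in 50 give an exact interval of 66% to 90%.

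**The case against.** The strongest reply is that this is a pilot sized for precision, that it says so, and that its intervals are calculated correctly. Much of that stands. Every printed interval reproduces, and the plan itself warns that intervals widen for rates away from 0% or 100%. Tolerability is the primary endpoint, and its commoner events would very likely appear. At the 6-day rates in section 10, the chance of no case in 50 is 1.5% for nausea (8%), 4.5% for headache (6%) and 13% for diarrhea (4%). The weak reassurance concerns the rarer toxicities.

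Four stronger readings may tempt a reader, and the documents do not support them.

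- **The trial has been shown to lack power.** With no criterion stated, power is undefined. It has not been shown to fall short.
- **The pilot label contradicts the claim outright.** The conflict is clear for efficacy, which is tertiary. For safety and tolerability, the declared focus, the sentence overstates more than it contradicts.
- **The 6-day rates can be scaled to 4 to 12 weeks.** Section 10 reports only a possible duration effect, and nothing supports a constant hazard. That assumption would also weaken the zero-count argument. Platelets at 2.3% per 6 days would become 1 − 0.977^(28/6) = 10.3% at 4 weeks, and P(0 in 50) would fall from 31% to 0.4%.
- **A zero count says almost nothing, or the hypotheses would be declared supported on one.** Zero in 50 does exclude rates above about 7%. The plan has no decision rule, and it promises confidence intervals for safety and efficacy.

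**Conclusion.** The claim of sufficient power is unsupported: no criterion, null rate or power value stands behind it, and the study is declared descriptive. The precision offered instead is arithmetically right but rests on a method that is too optimistic at low event counts. Its upper limit of 6.8% for a 2.5% event lies below the best exact two-sided limit that 50 subjects can give (7.1%), and a single event raises that limit to 10.6%.

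The zero-case probabilities of 78%, 55% and 31% assume 50 analysed subjects and the protocol's 6-day rates. True rates over 4 to 12 weeks are unknown and may be higher, in which case cases would be more likely to be seen. The exact limits in step 2 of the check do not depend on those rates.

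**What to change.** In section 9(i), replace the sentence that claims sufficient power with:

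> n=50 is a pilot size chosen for precision. With 0 events in 50 the exact two-sided 95% upper limit is 7.1%; with 1 event the interval is 0.05%-10.6%. There is a 95% chance of seeing at least one case only if the true rate is about 5.8% or more. The study is not powered to establish safety or efficacy.

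In the interval paragraph, and where it is repeated as the power analysis, specify exact intervals for low-incidence outcomes and remove the <0.1% to 6.8% example.

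The change is to protocol wording only: no extra subjects, visits or tests. The downside is that the stated assurance becomes less favourable.
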